### 6.3 Schedule of Assessments

For the complete schedule of assessments, refer to [Appendix A: Schedule of Events](#).

### 6.4 Treatments

#### 6.4.1 *Treatments Administered*

- ADU-S100 (MIW815; disodium dithio-(RP, RP)-[cyclic [A(2',5')pA(3',5')p]]), is a synthetic CDN composed of two adenosine monophosphate (AMP) analogues cyclized via a 2',5' (noncanonical) and a 3',5' (canonical) phosphodiester bond.

All lesions designated for ADU-S100 administration will be injected on Days 1 and 8 of each dosing cycle (ie, do not rotate/alternate sites for injection; all designed lesions will be injected on every dosing day).

- Pembrolizumab is an immunoglobulin G4 (IgG4) kappa immunoglobulin with an approximate molecular weight of 146 kDa.

On dosing days where both pembrolizumab and ADU-S100 are indicated, the pembrolizumab infusion will be administered first, followed by an intratumoral injection of ADU-S100.

## 6.4.2 *Method of Assigning Subjects to Treatment Groups*

All subjects will be sequentially assigned a unique identification number during Screening. The study is designed as a single-arm study; all subjects will receive ADU-S100 and pembrolizumab as indicated.

## 6.5 **Efficacy and Safety Variables**

### 6.5.1 *Efficacy Variables*

#### 6.5.1.1 *Primary Efficacy Variable*

The primary efficacy endpoint is the objective response rate (ORR) defined as the proportion of subjects in whom a complete response (CR) or a partial response (PR) is observed. The Response Evaluation Criteria in Solid Tumors (RECIST) v1.1 will be used to evaluate the primary efficacy endpoint. All responses will be confirmed at the subsequent tumor assessment.

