#### 9.4.2.3 Regression of Injected Lesions

If a lesion shows signs of significant regression (i.e. shrinkage) that precludes the ability to re-inject the lesion, other accessible lesions may be injected after documented discussion between the Investigator and the Medical Monitor.

If the injected lesion(s) shows signs of significant regression such that only scar tissue is remaining, a PET scan should be performed to identify whether any tumor tissue remains. If no tumor tissue remains, administration of ADU-S100 at the lesion may be discontinued.

After all lesions that meet requirements in [Section 9.4.2.1](#) have been successfully treated, additional smaller lesions may be injected with ADU-S100 following consultation with the Medical Monitor.

If the injected lesion(s) shows signs of significant regression (i.e. shrinkage) such that repeat administration of ADU-S100 is no longer possible in any lesion, the subject will be scheduled to complete the EOT visit and may continue treatment with pembrolizumab as monotherapy/standard of care outside the context of the ADU-CL-20 clinical trial. Previously resolved injected lesions that recur can be re-injected as long as the subject has not met criteria for treatment discontinuation ([Section 8.3.2](#)).

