**Figure 1 ADU-CL-20 Study Design**

Subjects will be requested to complete multiple clinic visits during all dosing cycles. An end of treatment (EOT) visit will occur 30 (+7) days after the last dose of study drug. All EOT visit assessments will be completed prior to commencing any new anti-cancer therapy.

After completion of the EOT visit, follow-up visits will be conducted at 8-week intervals to satisfy protocol-specified safety reporting periods, and collect data on any subsequent cancer-related therapies as well as vital status. Follow-up visits may be conducted at the site or via telephone call, as appropriate.

Subjects who discontinue study drug early for reasons other than progressive disease will complete the EOT visit and will be asked to continue tumor response assessments. Follow-up visits will also be conducted at 8-week intervals for these subjects.

All study visits (and visit windows), assessments, and procedures will be performed as indicated in [Appendix A: Schedule of Events](#). On days when the study drug is administered, assessments will be performed prior to dosing unless otherwise specified.

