- Duration of Disease Control (DODC): defined as the time from the first tumor assessment that supports the subject's disease control (CR, PR, SD) to the time of disease progression or death due to any cause; if the subject has a best response of SD, then DODC is calculated from date of baseline tumor assessment to the time of disease progression or death due to any cause. For subjects who have ongoing disease control at the time of analysis, their DODC will be censored at the time of last evaluable tumor assessment. Subjects who receive anti-cancer therapy prior to documented disease progression will be censored on the date of last evaluable tumor assessment on or prior to the start date of the anti-cancer therapy. Subjects with no on-treatment tumor assessments will be censored on the date of treatment start.
- ORR per modified RECIST v1.1 for immune-based therapeutics (iRECIST), where all noted disease progression will be confirmed at the subsequent tumor assessment
- Occurrence and severity of treatment-emergent adverse events
- Changes from baseline in safety assessments
- Plasma concentration-time profiles and derived noncompartmental PK parameters (including  $C_{max}$ , area under curve [AUC])

Progression-free survival, DOR, DCR, and DODC will be determined per RECIST v1.1 and iRECIST. [Section 7.4.6.2](#) contains a full table of the censoring rules that will be used in these analyses. [Section 7.4.6.3](#) contains additional information regarding response assessment per iRECIST. [Section 7.4.6.8](#) contains additional information regarding subgroup analysis.

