#### 7.4.4 *Primary Efficacy Endpoint Analysis Methods*

The primary efficacy endpoint is ORR as defined in [Section 6.4.1.1](#) and will be summarized for the All Treated Population.

Summaries of ORR will include the number and percentage of subjects with an objective response and the corresponding two-sided 95% confidence interval (CI) based on the exact binomial method (Clopper-Pearson). Waterfall plots will be provided showing the best overall tumor response. A swimmer plot of disease status for RECIST and iRECIST will be provided. Also, a spider plot of percent change in tumor size relative to baseline will be provided.

Tumor diameters recorded on the Target and New Lesions CRF pages will be utilized for analysis summaries. Diameters recorded on the Dose Administration CRF page or the Injected Lesion Photo CRF page will not be utilized for analysis.

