**Table 3 Censoring Rules for OS, PFS, DOR, and DODC**

Endpoint	Situation	Date of Censoring
OS	No documentation of death	Date that the subject was last known to be alive
PFS, DODC	No progression and no death	Date of last evaluable tumor assessment
PFS, DODC	Anti-cancer therapy prior to documented disease progression	Date of last evaluable tumor assessment on or prior to the start date of the anti-cancer therapy
PFS, DODC, DOR	No on-treatment tumor assessment	Date of treatment start
DODC	Ongoing disease control at time of analysis	Date of last evaluable tumor assessment
DOR	Ongoing response	Date of last evaluable tumor assessment

No other missing data will be imputed.

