**FOOTNOTES FOR TABLE 2-1 (See Sections 9 and 10 for additional information)**

-  Cycle length is 21 days. If a dose of either study drug is delayed, shift scheduled assessments accordingly.
-  EOT Visit occurs 30 days (+7 days) after the last dose of study drug (ADU-S100 or standard of care (pembrolizumab) or prior to commencing new anti-cancer therapy.
-  Follow-up: Visit may be conducted at site or via phone for vital status assessment, any subsequent cancer-related therapies, and safety follow-up to complete required Safety Reporting Periods (Table 10-1), as indicated. Concomitant medications will only be collected if associated with the management of an ongoing AE or SAE, or if a new anti-cancer treatment. Continue imaging if a subject discontinues study treatment for reasons other than progressive disease per Section 10.2.1.
-  Demographics, Medical History, Height: includes date of birth, age, gender, ethnicity, and race. Medical history includes all active conditions and any condition considered to be clinically significant by the Investigator. Disease-specific details include date of diagnosis, primary tumor histology, prior surgery(ies), radiation therapy, chemo- and biological therapies, and stage of cancer. Obtain standing height.
-  Tumor imaging: See Section 10.2.1. Collect scans electronically; perform response assessments per RECIST 1.1 and iRECIST. Tumor assessments should be fixed according to calendar, regardless of treatment delays. After 45 weeks, the imaging frequency for all subjects will be performed at a Q12W (-14 days) frequency until confirmed disease progression, withdrawal, or study end. If a subject discontinues study treatment for reasons other than progressive disease and has not received other anti-cancer therapy, continue imaging at designated frequency. Perform at EOT if more than 6 weeks have passed since last evaluation.
-  Vital Signs: Blood pressure, pulse, respiratory rate, and temperature. Cycles 1 and 2: scheduled time points relative to the start of the pembrolizumab infusion (Day 1) = pre-dose, end of infusion; scheduled time points relative to the start of the ADU-S100 injection (Days 1, 8) = pre-dose, 3 hours and 6 hours post-dose. On all other dosing days, perform vital sign assessment prior to the start of each study drug or more frequently as clinically indicated.

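### Does the primary ORR need a written rule for a CR or PR that has no later scan?

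*SAP*

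**What the plan says.** SAP 6.5.1.1 defines ORR as the proportion of subjects "in whom a complete response (CR) or a partial response (PR) is observed" under RECIST v1.1, and closes with "All responses will be confirmed at the subsequent tumor assessment". SAP 7.4.4 takes its definition from there ("The primary efficacy endpoint is ORR as defined in" a section numbered 6.4.1.1, evidently meaning 6.5.1.1). It reports the count, percentage and Clopper-Pearson 95% interval in the All Treated Population. Protocol 12.5.1 does not mention confirmation. Protocol Appendix B, below the overall-response table, says regressions should be confirmed at the next assessment. SAP 7.4.6.2 ends, under Table 3, with "No other missing data will be imputed".

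On exit for regression, Protocol 9.4.2.3 says that once no lesion can be injected, "the subject will be scheduled to complete the EOT visit and may continue treatment with pembrolizumab as monotherapy/standard of care outside the context" of the trial. Protocol Table 2-1 places EOT 30 to 37 days after the last dose, calls for an EOT scan only when more than 6 weeks have passed since the last one, and has no column after EOT. The SAP says more. In SAP 6.1, subjects stopping early for reasons other than progression "will complete the EOT visit and will be asked to continue tumor response assessments". SAP Appendix A, footnote 5, says "If a subject discontinues study treatment for reasons other than progressive disease and has not received other anti-cancer therapy, continue imaging at designated frequency".

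For iRECIST ORR, SAP 6.5.1.2 asks for confirmation of progression only: "where all noted disease progression will be confirmed at the subsequent tumor assessment".

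**The concern.** An observed response and a confirmed response give different counts for a subject whose CR or PR is never re-imaged, and no sentence says which applies. The protocol can produce such subjects through success. Regression leaves nothing to inject, the subject goes to EOT, and EOT may come too soon for a scan to be due. Read strictly, that subject stays in the denominator, leaves the numerator, and drops out of the duration-of-response analysis. ORR would then be biased downward by the effect it is meant to measure. If the choice stays open until the data are seen, it becomes the kind of post hoc decision that the SAP introduction says it is written to avoid. The RECIST and iRECIST rates could also differ through confirmation rules alone.

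**Working it through.** The plan gives no figure of its own on this point, so the check has four parts: which reading the text supports, when a confirming scan is due, what one subject is worth, and what the reader will see.

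**1. Which reading the text supports.** If observed alone were enough, the closing sentence of SAP 6.5.1.1 would do nothing. If confirmation is required, both sentences have a job: a CR or PR is seen, then confirmed. Appendix B of the protocol agrees. The no-imputation line follows a censoring table for secondary endpoints, but it closes the section on dropouts and missing data, and its wording reaches beyond that table. With no confirming scan and nothing imputed, there is no confirmed response. The denominator is fixed by SAP 7.2 and 7.4.4.

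**2. When an EOT scan is due.** Let L be the days from response scan to last dose (negative if the last dose came first). EOT falls L + 30 to L + 37 days after the scan, and a scan is due if that exceeds 42.

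- L of 5 or less: at most 5 + 37 = 42, so never due.
- L of 6 to 12: due on some EOT days only (6 + 37 = 43, but 12 + 30 = 42).
- L of 13 or more: at least 13 + 30 = 43, so always due.

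On nominal dosing days, with C1D1 as Day 1, the first scan falls on Days 57 to 64:

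| Last dose | Day | EOT days | Days from scan to EOT | Scan due? |
|---|---|---|---|---|
| C3D8 | 50 | 80–87 | 16–30 | No |
| C4D1 | 64 | 94–101 | 30–44 | Only at 43–44 |
| C5D1 | 85 | 115–122 | 51–65 | Yes |

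This assumes EOT is not brought forward for new therapy, which would shorten the gap. The gap in the schedule is therefore real, but it closes once dosing has gone on about two weeks past the response scan. These are date ranges, not probabilities.

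**3. What one subject is worth.** One response is 1/20 = 5.0 points at the planned size, or 1/16 = 6.25 points at the 16 subjects treated by 17 December 2020 (Protocol 5.2.2). The response counts below are assumed for illustration:

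| Counted | ORR | Exact 95% CI |
|---|---|---|
| 8/20 | 40.0% | 19.1–63.9% |
| 7/20 | 35.0% | 15.4–59.2% |
| 5/20 | 25.0% | 8.7–49.1% |
| 4/20 | 20.0% | 5.7–43.7% |

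At 8/20 the interval is 63.9 − 19.1 = 44.8 points wide, about nine times the shift from one subject.

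**4. What the reader will see.** SAP 7.4.4 plans a waterfall plot of best response, a swimmer plot of disease status under RECIST and iRECIST, and a spider plot of tumor size. SAP 7.1.1 lists the data by subject. With about 20 subjects, each CR or PR and any scan after it can be identified, so either rate can be recovered.

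**The case for a change.** The strongest case is that the text leans towards an answer without stating it, that the numerator of a primary endpoint should not rest on inference, and that any loss falls on subjects who did well. One subject can matter to the eye: from 8/20 to 7/20 the lower limit moves from just above the 19% reference rate to below it. The SAP's continued imaging may not rescue these subjects either, because pembrolizumab taken outside the trial might be read as other anti-cancer therapy under footnote 5.

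Part of this stands. No sentence classifies an unconfirmed RECIST response, and a confirmed rate can only err downward here.

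The rest is weaker. The bias needs imaging to stop at EOT, and the text does not settle that. The continuation wording in SAP 6.1 carries no condition about other therapy. Protocol Table 2-1, footnote 5, fixes assessments to the calendar and, after 27 weeks, runs them to confirmed progression, withdrawal or study end. Protocol 8.3.2 says stopping treatment is not automatic withdrawal from the study. The exit itself is uncommon by design, since Protocol 9.4.2.1 and 9.4.2.3 let other lesions, including smaller ones, be injected first. Crossing 19% triggers nothing: SAP 7.4.6.6 makes results descriptive with no formal comparisons, and Protocol 12.1 holds enrollment at about 20.

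Possible additions gain little. A second ORR row or a flag would leave the primary result unchanged. Letting any EOT scan count as confirmation would be worse, since on the C3D8 path an optional scan could come 16 days after the response. The iRECIST basis can already be read from SAP 6.5.1.2 and Table 4, where an iCR or iPR followed by a non-evaluable scan keeps its category. Two separately defined criteria may differ without either being wrong.

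**Conclusion.** No change is called for. This is missing detail that an analyst would fill sensibly, not a stated rule shown to give a wrong result. The natural reading is a confirmed ORR in which a CR or PR without a later scan is not counted, and its error, if any, does not flatter the treatment. The size is 5.0 points per affected subject at n = 20. The number affected cannot be derived because neither document gives an exit rate, and it may be zero. The 6.4.1.1 reference is a clerical slip, as SAP 6.4.1 describes treatments. The difference in post-EOT imaging text is a separate matter of version alignment: the SAP still describes 34 subjects, 8-weekly follow-up visits and a switch to 12-weekly imaging after 45 weeks, where the protocol has about 20 subjects, no visits after EOT and 27 weeks. That mismatch affects whether a confirming scan exists, not how a response without one is counted. The conclusion rests on the analysis staying descriptive and on the planned plots and listings being produced.

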#### 6.5.1.2 *Secondary Efficacy Variables*

Secondary efficacy endpoints include the following:

- Overall Survival (OS): defined as the time from first dose of either study drug until date of death due to any cause. Subjects without documentation of death at the time of analysis will be censored as of the date the subject was last known to be alive.
- Progression-Free Survival (PFS): defined as the time from first dose of either study drug to first documentation of disease progression or death due to any cause. Subjects who do not experience progressive disease and are alive at the time of analysis will be censored at the time of last evaluable tumor assessment. Subjects who receive anti-cancer therapy prior to documented disease progression will be censored on the date of last evaluable tumor assessment on or prior to the start date of the anti-cancer therapy. Subjects with no on-treatment tumor assessments will be censored on the date of treatment start.
- Duration of Response (DOR): defined as the time from the first tumor assessment that supports the subject's objective disease response to the time of disease progression or death due to any cause. Subjects who have ongoing response at the time of analysis will be censored at the time of last evaluable tumor assessment. Subjects who receive anti-cancer therapy prior to documented disease progression will be censored on the date of last evaluable tumor assessment on or prior to the start date of the anti-cancer therapy. Subjects with no on-treatment tumor assessments will be censored on the date of treatment start.
- Disease Control Rate (DCR): defined as the proportion of subjects with CR, PR, or stable disease (SD).

- Duration of Disease Control (DODC): defined as the time from the first tumor assessment that supports the subject's disease control (CR, PR, SD) to the time of disease progression or death due to any cause; if the subject has a best response of SD, then DODC is calculated from date of baseline tumor assessment to the time of disease progression or death due to any cause. For subjects who have ongoing disease control at the time of analysis, their DODC will be censored at the time of last evaluable tumor assessment. Subjects who receive anti-cancer therapy prior to documented disease progression will be censored on the date of last evaluable tumor assessment on or prior to the start date of the anti-cancer therapy. Subjects with no on-treatment tumor assessments will be censored on the date of treatment start.
- ORR per modified RECIST v1.1 for immune-based therapeutics (iRECIST), where all noted disease progression will be confirmed at the subsequent tumor assessment
- Occurrence and severity of treatment-emergent adverse events
- Changes from baseline in safety assessments
- Plasma concentration-time profiles and derived noncompartmental PK parameters (including  $C_{max}$ , area under curve [AUC])

Progression-free survival, DOR, DCR, and DODC will be determined per RECIST v1.1 and iRECIST. [Section 7.4.6.2](#) contains a full table of the censoring rules that will be used in these analyses. [Section 7.4.6.3](#) contains additional information regarding response assessment per iRECIST. [Section 7.4.6.8](#) contains additional information regarding subgroup analysis.

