### 12.5.2 Secondary Efficacy Endpoints

Secondary efficacy endpoints are defined as:

**Overall Survival (OS)** is defined as the time from first dose of study drug until date of death due to any cause. Subjects without documentation of death at the time of analysis will be censored as of the date the subject was last known to be alive.

**Progression-free survival (PFS)** is defined as the time from first dose of study drug to first documentation of disease progression or death due to any cause. Subjects who do not experience progressive disease and are alive will be censored at the time of last evaluable tumor assessment.

**Duration of response (DOR)** is defined as the time from the first tumor assessment that supports the subject's objective disease response to the time of disease progression or death due to any cause.

**Disease control rate (DCR)** is defined as subjects with CR, PR, or stable disease (SD).

**Duration of disease control (DODC)** is defined as the time from the first tumor assessment that supports the subject's disease control (CR, PR, SD) to the time of disease progression or death due to any cause.

**ORR** per iRECIST

RECIST v1.1 and iRECIST will be used for all secondary efficacy endpoints, as applicable. Estimates of PFS and OS will be assessed using Kaplan-Meier methodology.

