#### 7.4.5 *Secondary Endpoint Analysis Methods*

The calculation of ORR and accompanying CI will be repeated for the EAS. The secondary efficacy endpoints described in [Section 6.4.1.2](#) will be summarized for the All Treated Population.

Overall survival and PFS will be analyzed with standard survival methods (Kaplan-Meier estimates) to include the number of subjects who are alive at data cut-off, number of subjects censored, percentiles (including 95% CIs determined by the Brookmeyer and Crowley method) and range. Kaplan-Meier summaries, including graphs of survival curves, will be generated for all subjects receiving study drug.

Progression-free survival at 6, 12, and 24 months (including 95% CIs determined by Greenwood’s formula), DOR, and DODC will be analyzed with the same statistical methodologies as applied to OS.

DCR will be calculated along with accompanying CIs, similar to ORR.

Censoring rules for the analysis of each endpoint are described in [Section 7.4.6.2](#). Subgroup analysis is described in [Section 7.4.6.8](#).

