## APPENDIX A: SCHEDULE OF EVENTS

**Table 2-1 Schedule of Events**

Study Period	Screening	Treatment Period						EOT 	Follow Up 
		Cycle 1			Cycle 2 and Beyond				
Cycle Day (21-day cycles) 	-28 to -1	1	2	8	1	8	30 d post last dose	Q8W after EOT visit	
Visit Window (days)	-	-	-	±1	±1 (±3 Cycles 3-7; ±5 Cycles 8+)	±1 (±3 Cycles 3-7; ±5 Cycles 8+)	+7	+7	
Informed consent	X								
Demographics, Medical history, Height 	X								
Inclusion/Exclusion criteria	X								
SAFETY & EFFICACY EVALUATIONS									
Tumor imaging & response assessment 	X				Cycle 4 Day 1 (-7 days), Q9W (-14 days) thereafter 				
Photography of injected lesions		(pre-dose)			(pre-dose)		X		
Vital status (survival), Current cancer therapy							X	X	
ECOG performance status	X	X			X		X		
Vital signs 	X	X	X	X	X	X	X		
Physical examination, Weight 	X	X			X		X		
Electrocardiogram 	X	X		X	Cycles 2-3		X		
Adverse events 	X	X	X	X	X	X	X	X	
Prior and Concomitant medications	X	X	X	X	X	X	X	X 	
LABORATORY ASSESSMENTS (obtain prior to dosing unless otherwise indicated)									
Virology, Serology 	X								
Urinalysis, Coagulation panel 	X				As clinically indicated				
Hematology, Chemistry 	X	X 		X	X 		X		
Thyroid function 	X	X 			odd cycles 		X		
Pregnancy (WOCBP) 	Serum	Serum			X		X		
Plasma cytokines (safety) 	X	As clinically indicated for CRS initial diagnosis & follow up monitoring							
ADU-S100 PK (plasma) 		X		X	Cycle 2				
Plasma cytokines (research) 	X	X	X	X 	X 		X 	if at site 	
Whole blood (PGx) 		X							
Whole blood (transcriptomics) 	X	X	X	X	X 		X 	if at site 	
Whole blood (PBMC; select sites only) 	X	X	X	X	Cycles 2-3		X 	if at site 	
Tumor tissue (lesion for injection) 	X			X			C2D15 (±3)	Optional 	
Tumor tissue (non-injected lesion) 	X						C2D15 (±3)	Optional 	
STUDY DRUG ADMINISTRATION									
Pembrolizumab (IV infusion) 		X			X				
ADU-S100 (intratumoral injection) 		X 		X	X	X			

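### The PFS rule for subjects with no on-treatment scan does not exclude deaths, so an early unscanned death can be censored at day 1 instead of counted as an event

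*SAP*

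**What the plan says.** In SAP 6.5.1.2, PFS as an endpoint is "defined as the time from first dose of either study drug to first documentation of disease progression or death due to any cause". Anyone alive and without progression at the analysis is censored at the last evaluable assessment. A further sentence censors those who start other anti-cancer therapy before progression. The bullet then closes: "Subjects with no on-treatment tumor assessments will be censored on the date of treatment start".

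Table 3 repeats this in a row labelled "No on-treatment tumor assessment", which covers PFS, DODC and DOR and gives treatment start as the censoring date. The general PFS/DODC row of the same table is labelled "No progression and no death". The closing paragraph of 6.5.1.2 says that section 7.4.6.2, where Table 3 sits, "contains a full table of the censoring rules that will be used in these analyses".

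Protocol 12.5.2 has the same event definition and one censoring rule: "Subjects who do not experience progressive disease and are alive will be censored at the time of last evaluable tumor assessment". It has no rule for subjects without a scan.

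SAP 7.4.5 analyses PFS in the All Treated Population and reports Kaplan-Meier percentiles and "Progression-free survival at 6, 12, and 24 months". SAP 7.6 lists the changes from the protocol (EAS definition, analysis population, DODC start date for stable disease). The no-scan rule is not among them.

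**The concern.** The no-scan rule has no vital-status condition. For a subject who dies without an on-treatment scan, the event definition gives an event on the date of death, and the no-scan rule gives censoring at treatment start. SAP 7.4.5 and 7.4.6.2 do not say which comes first. The wording of Table 3 makes the gap harder to read away, because one PFS row excludes deaths explicitly and the other does not.

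Such subjects are foreseeable. All treated subjects enter the PFS analysis, and the SAP's EAS definition names death as an alternative to having an evaluable response assessment. Protocol Appendix D also ranks tumor imaging last of six priorities when site staff are limited.

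At stake is a bias in one direction. Censoring at day 1 treats an early death as a subject about whom nothing is known, which raises the PFS curve from then on. It can also produce an impossible result, with PFS above OS, because OS counts the same death. The SAP's introduction says it describes the analyses so as to avoid post hoc decisions; as written, the coding of these deaths would be one.

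**Working it through.** The plan states no PFS target, event count or power, so there is no figure to reproduce. The check sets the rules side by side and then measures the difference between them.

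**1. Coding of a death with no on-treatment scan**

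| Source | Result |
|---|---|
| SAP 6.5.1.2, event definition | Event on date of death |
| Protocol 12.5.2 | Event on date of death |
| SAP 6.5.1.2, last sentence of the PFS bullet | Censored at treatment start |
| SAP Table 3, no-scan row | Censored at treatment start |

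Under the duration convention in SAP 7.1.4 (later date − earlier date + 1), censoring at treatment start gives a PFS time of 1 day.

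**2. Period at risk.** The schedule gives the first on-treatment scan as "Cycle 4 Day 1 (-7 days), Q9W (-14 days"). With 21-day cycles, Cycle 4 Day 1 is day 1 + 3 × 21 = 64, and the 7-day window opens on day 57. A subject who dies before then without an unscheduled scan falls under the rule.

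**3. Effect on Kaplan-Meier PFS.** Let k of N treated subjects die unscanned, let m(t) be the number event-free at time t (after those deaths), and assume no other censoring before t and no event on day 1.

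- Deaths as events: S(t) = m(t)/N.
- Deaths censored at day 1: S(t) = m(t)/(N − k).
- Ratio: N/(N − k), whatever the order of the later events.

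| N | k = 1 | k = 2 | k = 4 |
|---|---|---|---|
| 20 (planned size) | 20/19 = 1.05 | 20/18 = 1.11 | 20/16 = 1.25 |
| 16 (treated as of 17 Dec 2020, protocol 5.2.2) | 16/15 = 1.07 | 16/14 = 1.14 | 16/12 = 1.33 |

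The documents do not give k; 1 to 4 is an assumed range.

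**4. In percentage points.** Assume that 8 of 20 subjects are event-free at 6 months, so PFS by the definition is 8/20 = 40%. The literal rule gives 8/19 = 42.1%, 8/18 = 44.4% and 8/16 = 50.0% for k = 1, 2 and 4. The standard error of the 40% is √(0.4 × 0.6/20) = 0.110, about 11 points.

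**5. PFS against OS.** With k = 2 of 20 and no other event by week 8, OS is 18/20 = 90%. PFS under the literal rule is 18/18 = 100%.

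**6. Overlap with the new-therapy rule.** Take an unscanned subject who starts other anti-cancer therapy and then dies. The new-therapy row points to the last evaluable assessment, which here is the baseline scan (day −28 to −1), before the PFS time origin. The no-scan row points to treatment start, and the event definition points to the date of death. No order is stated.

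**The case against.** The strongest reply is that events come first by convention. Death is defined as a PFS event, censoring rules apply only to subjects without one, and Table 3 sits under a heading about dropouts and missing data, which an observed death is not. On that reading the no-scan row only supplies a date for living subjects. This is a sensible reading, and a careful programmer might follow it. But the SAP does not state it, and the contrast between the two Table 3 rows tells against it.

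Omission from SAP 7.6 is weak evidence of an undisclosed change. The protocol leaves missing-data handling to the SAP, and the new-therapy rule is likewise absent from both protocol 12.5.2 and SAP 7.6. That is fair: the rule departs from the protocol only if it is applied to deaths.

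The size is hypothetical. No early deaths are reported, eligibility requires ECOG 0 or 1, and treated N may exceed 20 because that figure is the evaluable target. Protocol 10.2.1.1 asks for prompt imaging when progression is suspected, and an EOT scan is due if more than 6 weeks have passed since the last one. Both routes lower k, and progression on such a scan, or death after it, still counts. For k = 1 or 2 the shift of 2 to 4 points is well inside the standard error. All of this stands and limits the weight of the point, but it does not settle how an unscanned death is coded.

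It can also be said that the no-scan row already supplies a date for an unscanned subject who starts new therapy. That is true of the current wording. Once the row is limited to subjects who have not died, it no longer covers one who starts new therapy and then dies, so the order must be written down.

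**Conclusion.** The concern holds. The no-scan rule as written conflicts with the SAP's own PFS definition and with protocol 12.5.2, and following it literally biases PFS upward.

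The size is a factor of N/(N − k) on every PFS estimate after the unscanned deaths: 5% to 25% in relative terms for 1 to 4 such deaths among 20. This rests on no other censoring before the time in question and on an assumed k. The effect is zero if k = 0.

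The scope is limited to PFS, a descriptive secondary endpoint with no formal comparison attached. The listing of DOR and DODC in the no-scan row changes no result, since an unscanned subject has no assessment that supports response or disease control. The point should be corrected before database lock because the bias runs in the favourable direction and the remedy is simple.

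**What to change.** In SAP 6.5.1.2 and Table 3:

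- Limit the PFS no-scan rule to subjects with no on-treatment assessment who have not died; they remain censored at treatment start.
- State that a death with no earlier on-treatment assessment is a PFS event on the date of death.
- State which rule governs when such a subject started other anti-cancer therapy before dying. If it is the new-therapy rule, give a censoring date that does not precede the first dose when the only scan is baseline.
- As tidying, remove DOR and DODC from the no-scan row and delete the matching sentence from their bullets.
- Align the wording with protocol 12.5.2 and record any intended departure in SAP 7.6.

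The cost is a few sentences and one table row before database lock, with no new data. Reported PFS may be slightly less favourable.
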